# LIST OF ABBREVIATIONS AND DEFINITIONS OF TERMS

Abbreviation	Definition
AE	Adverse Event
ANCOVA	Analysis of Covariance
ARDS	Acute Respiratory Distress Syndrome
ATC	Anatomical Therapeutic Chemical
BMI	Body Mass Index
COVID-19	Severe Acute Respiratory Syndrome Coronavirus 2 (SARS-CoV-2)
CSR	Clinical Study Report
CT	Computed Tomography
ECG	Electrocardiogram
ECMO	Extracorporeal Membrane Oxygenation
eCRF	Electronic Case Report Form
ICU	Intensive Care Unit
ITT	Intent-to-Treat
MedDRA	Medical Dictionary of Regulated Activities
mITT	Modified Intent-to-Treat
MMRM	Mixed Model for Repeated Measures
PRN	Pro re nata – As Needed
RRT	Renal Replacement Therapy
SAE	Serious Adverse Event
SARS-CoV-2	Severe Acute Respiratory Syndrome Coronavirus 2
$SpO_2$	Capillary Oxygen Saturation
TEAE	Treatment Emergent Adverse Event
WHO	World Health Organization

QMD Ref: Worldwide-TMP-ST-005-7.0 Effective: 12Aug2019	Governing QMD: Worldwide-SOP-ST-001
--	-------------------------------------

Worldwide Clinical Trials Controlled Quality Management Document			
WORLDWIDE CLINICAL TRIALS	Sponsor:	Veru Inc.	
CLINICAL TRIALS	Protocol Number:	V0211901	
STATISTICAL ANALYSIS PLAN. PHASE 2-3-4			

#### 1 INTRODUCTION

This document details the planned statistical analyses for Veru Inc., protocol "V0211901" study titled "Randomized, Placebo-Controlled, Phase 2 Study of VERU-111 for the Treatment of Severe Acute Respiratory Syndrome Coronavirus 2 (SARS-CoV-2) in Patients at High Risk for Acute Respiratory Distress Syndrome (ARDS)".

The proposed analyses are based on the contents of the final version of the protocol (version 7.0, dated 25-SEP-2020). IND number: 149282.

This study is a multicenter, randomized, double-blind, placebo-control, efficacy and safety study of VERU-111 for the treatment of COVID-19.

This study consists of two treatment arms: VERU-111 18 mg treated group, and Placebo treated Group. Subjects will be randomized in a 1:1 fashion.

Subjects in the VERU-111 treatment group will receive standard of care, plus oral daily VERU-111 18 mg for 21 days or until released from hospital.

Subjects in the Placebo treatment group will receive standard of care, plus a placebo capsule for 21 days or until released from hospital.

VERU-111 18 mg dose will be supplied as capsules containing 18 mg of VERU-111. Capsules will be supplied in bottles containing 21 capsules in each bottle. Subjects will take one VERU-111 capsule per day.

Placebo capsules containing zero (0) mg VERU-111 drug substance will be supplied in bottles containing 21 capsules each. The placebo capsules will contain only anhydrous lactose, USP. These capsules are identically appearing to the VERU-111 capsules. Subjects will take one Placebo capsule per day.

#### 2 STUDY OBJECTIVES

# 2.1 Primary Objective

To demonstrate the efficacy of VERU-111 in the treatment of SARS-CoV-2 infection by assessing its effect on the proportion of subjects that are alive without respiratory failure at Day 29. Respiratory failure is defined as endotracheal intubation and mechanical ventilation, extracorporeal membrane oxygenation, high-flow nasal cannula oxygen delivery, noninvasive

QMD Ref: Worldwide-TMP-ST-005-7.0 Effective: 12Aug2019	Governing QMD: Worldwide-SOP-ST-001		
Confidentiality Statement			
This document is the property of Worldwide Clinical Trials Inc. and may not be duplicated, copied, altered or removed from company without			
prior approval from Worldwide Quality Assurance or in compl	liance with Worldwide Standard Operating Procedures		

# Worldwide Clinical Trials Controlled Quality Management Document | Sponsor: | Veru Inc. | | Protocol Number: | V0211901 | | STATISTICAL ANALYSIS PLAN. PHASE 2-3-4

positive pressure ventilation, clinical diagnosis of respiratory failure with initiation of none of these measures only when clinical decision making is driven solely by resource limitation.

# 2.2 Secondary Objectives

Secondary objectives of the study are:

- 1. World Health Organization (WHO) Ordinal Scale for Clinical Improvement (8-point ordinal scale) at Day 15, Day 22, and Day 29
  - a. Change in mean WHO Ordinal Scale for Clinical Improvement at Day 15
  - b. Change in mean WHO Ordinal Scale for Clinical Improvement at Day 22
  - c. Change in mean WHO Ordinal Scale for Clinical Improvement at Day 29
  - d. Proportion of subjects that are Grade 5, 6, 7, or 8 on the WHO Ordinal Scale for Clinical Improvement at Day 15
  - e. Proportion of subjects that are Grade 5, 6, 7, or 8 on the WHO Ordinal Scale for Clinical Improvement at Day 22
  - f. Proportion of subjects that are Grade 5, 6, 7, or 8 on the WHO Ordinal Scale for Clinical Improvement at Day 29
- 2. Proportion of subjects with normalization of fever and oxygen saturation through Day 15, Day 22, and Day 29
- 3. Days on mechanical ventilation
- 4. All-cause mortality at Day 15, Day 22, and Day 29
- 5. Proportion of subjects alive and free of respiratory failure at Day 15, Day 22
- 6. Proportion of subjects alive and discharged from the ICU at Day 15, Day 22, and Day 29
- 7. Proportion of subjects alive and discharged from hospital at Day 15, Day 22, and Day 29
- 8. Days in Intensive Care Unit (ICU)
- 9. Days in hospital
- 10. Proportion of subjects on mechanical ventilation at Day 15, Day 22, and Day 29
- 11. Assess the pharmacokinetics of VERU-111 on Day 15.

# 2.3 Safety Objectives

To assess the safety and tolerability of VERU-111.

#### 3 ENDPOINTS

# 3.1 Primary Endpoint

QMD Ref: Worldwide-TMP-ST-005-7.0 Effective: 12Aug2019	Governing QMD: Worldwide-SOP-ST-001		
Confidentiality Statement			
This document is the property of Worldwide Clinical Trials Inc. and may not be duplicated, copied, altered or removed from company without			
prior approval from Worldwide Quality Assurance or in compliance with Worldwide Standard Operating Procedures			

# WORLDWIDE STATISTICAL ANALYSIS PLAN. PHASE 2-3-4

The primary endpoint for the study is the proportion of subjects that are alive without respiratory failure at Day 29. Respiratory failure is defined as endotracheal intubation and mechanical ventilation, extracorporeal membrane oxygenation, high-flow nasal cannula oxygen delivery, noninvasive positive pressure ventilation, clinical diagnosis of respiratory failure with initiation of none of these measures only when clinical decision making is driven solely by resource limitation.

# 3.2 Secondary Endpoints

The secondary endpoints on this study are:

1. WHO Ordinal Scale for Clinical Improvement (8-point ordinal scale):

Patient State	Descriptor	Score
Uninfected	No clinical or virological evidence of infection	0
Ambulatory	No limitation of activities	1
	Limitation of activities	2
Hospitalized, Mild disease	Hospitalized, no oxygen therapy	3
	Oxygen by mask or nasal prongs	4
Hospitalized, Severe disease	Non-invasive ventilation or high- flow oxygen	5
	Intubation and mechanical ventilation	6
	Ventilation + additional organ support – pressors, Renal Replacement Therapy (RRT), Extracorporeal Membrane Oxygenation (ECMO)	7
Death	Death	8

2. Proportion of subjects that are Grade 5, 6, 7, or 8 on the WHO Ordinal Scale for Clinical Improvement at Day 15

QMD Ref: Worldwide-TMP-ST-005-7.0 Effective: 12Aug2019 Governing QMD: Worldwide-SOP-S		
Confidentiality Statement		
This document is the property of Worldwide Clinical Trials Inc. and may not be duplicated, copied, altered or removed from company without		
prior approval from Worldwide Quality Assurance or in compliance with Worldwide Standard Operating Procedures.		

Worldwide Clinical Trials Controlled Quality Management Document			
WORLDWIDE	Sponsor:	Veru Inc.	
CLINICAL TRIALS	Protocol Number:	V0211901	
STATISTICAL ANALYSIS PLAN, PHASE 2-3-4			

- 3. Proportion of subjects that are Grade 5, 6, 7, or 8 on the WHO Ordinal Scale for Clinical Improvement at Day 22
- 4. Proportion of subjects that are Grade 5, 6, 7, or 8 on the WHO Ordinal Scale for Clinical Improvement at Day 29
- 5. Change in mean WHO Ordinal Scale for Clinical Improvement at Day 15
- 6. Change in mean WHO Ordinal Scale for Clinical Improvement at Day 22
- 7. Change in mean WHO Ordinal Scale for Clinical Improvement at Day 29
- 8. Proportion of subjects with normalization of fever and oxygen saturation through Day 15. This will be a composite of fever normalization maintained for at least 24 hours AND peripheral capillary oxygen saturation (SpO2) >94% sustained for 24 hours.
- 9. Proportion of subjects with normalization of fever and oxygen saturation through Day 22. This will be a composite of fever normalization maintained for at least 24 hours AND peripheral capillary oxygen saturation (SpO2) >94% sustained for 24 hours.
- 10. Proportion of subjects with normalization of fever and oxygen saturation through Day 29. This will be a composite of fever normalization maintained for at least 24 hours AND peripheral capillary oxygen saturation (SpO2) >94% sustained for 24 hours.
- 11. Days on mechanical ventilation
- 12. All-cause mortality at Day 15
- 13. All-cause mortality at Day 22
- 14. All-cause mortality at Day 29
- 15. Proportion of subjects alive and free of respiratory failure at Day 15
- 16. Proportion of subjects alive and free of respiratory failure at Day 22
- 17. Proportion of subjects alive and discharged from the ICU at Day 15
- 18. Proportion of subjects alive and discharged from the ICU at Day 22
- 19. Proportion of subjects alive and discharged from the ICU at Day 29
- 20. Proportion of subjects alive and discharged from hospital at Day 15
- 21. Proportion of subjects alive and discharged from hospital at Day 22
- 22. Proportion of subjects alive and discharged from hospital at Day 29
- 23. Days in ICU
- 24. Days in hospital
- 25. Proportion of subjects on mechanical ventilation at Day 15
- 26. Proportion of subjects on mechanical ventilation at Day 22
- 27. Proportion of subjects on mechanical ventilation at Day 29
- 28. Pharmacokinetics of VERU-111 on Day 15.

QMD Ref: Worldwide-TMP-ST-005-7.0 Effective: 12Aug2019	Governing QMD: Worldwide-SOP-ST-001
Confidentiality Statement	
This document is the property of Worldwide Clinical Trials Inc. and may not be duplicated, copied, altered or removed from company without	
prior approval from Worldwide Quality Assurance or in compliance with Worldwide Standard Operating Procedures.	

Worldwide Clinical Trials Controlled Quality Management Document		
WORLDWIDE CLINICAL TRIALS	Sponsor:	Veru Inc.
	Protocol Number:	V0211901
STATISTICAL ANALYSIS PLAN. PHASE 2-3-4		

# 4 SAMPLE SIZE

In the Phase 2, there are no power calculations done to determine the sample size. The Phase 2 study is intended as a proof-of-concept study only.

#### 5 RANDOMIZATION

Approximately, 40 subjects are planned to be randomized at a 1:1 ratio into two treatment arms (20 subjects in the VERU-111 treated group and 20 subjects in the Placebo treated group).

The subjects with documented evidence of COVID-19 infection (by standard diagnostic method) with symptoms for less than 8 days will be enrolled. Subjects will be at high risk for the development of ARDS.

#### 6 PLANNED ANALYSES

No statistical analysis plan (SAP) prepared in advance of the data can be absolutely definitive and the final Clinical Study Report (CSR) may contain additional tables or statistical tests if warranted by the data obtained. The justification for any such additional analyses will be fully documented in the final CSR.

### **6.1** Analysis Populations

Subjects excluded from the analysis populations and the reason for their exclusion will be listed in Appendix 16.2 of the CSR.

# **6.1.1** Enrolled Population

All subjects who gave informed consent.

# 6.1.2 Randomized Population

All enrolled subjects who were randomized to study treatment.

# 6.1.3 Intent-to-Treat (ITT) Population

All randomized subjects regardless whether the subject took the study drug or not. The ITT population will be used as the safety population.

# **6.1.4** Modified Intent-to-Treat (mITT) Population

All enrolled subjects who have taken at least 7 doses of study drug.

QMD Ref: Worldwide-TMP-ST-005-7.0 Effective: 12Aug2019	Governing QMD: Worldwide-SOP-ST-001
Confidentiality Statement	
This document is the property of Worldwide Clinical Trials Inc. and may not be duplicated, copied, altered or removed from company without prior approval from Worldwide Quality Assurance or in compliance with Worldwide Standard Operating Procedures.	

Worldwide Clinical Trials Controlled Quality Management Document		
WORLDWIDE CLINICAL TRIALS	Sponsor:	Veru Inc.
	Protocol Number:	V0211901
STATISTICAL ANALYSIS PLAN. PHASE 2-3-4		

# 6.1.5 Efficacy Evaluable (EE) Population

All ITT subjects excluding those subjects who were identified as non-compliant to study procedures. These subjects will be identified together with reason for exclusion in the subject evaluability form which will be signed prior to the database lock.

#### 6.2 Derived Data

This section describes the derivations required for statistical analysis. Unless otherwise stated, variables derived in the source data will not be re-calculated.

#### 6.2.1 Baseline

Baseline is defined as the last non-missing value (either scheduled, unscheduled or repeat) before the subject receives the first dose of study drug.

# **6.2.2 Duration / Study Day / Time**

Study day will be calculated as the number of days from first dose of study drug.

- date of event date of first dose of study drug + 1, for events on or after first dose
- date of event date of first dose of study drug, for events before first dose

# **6.2.3** Conventions for Missing and Partial Dates

All rules explained below for partial / missing dates will be followed unless contradicted by any other data recorded on the electronic Case Report Form (eCRF).

All dates presented in the individual subject listings will be as recorded on the eCRF (i.e., not completed as per the below rules).

# 6.2.4 Missing / Partial Start / Stop Date of Concomitant Medications

Missing and partial start and stop date will be imputed for analysis purposes as follows.

### Partial or missing stop date will be imputed as follows:

If the stop date is completely missing and the event has resolved, or the subject has stopped taking the concomitant medication, the stop date will be imputed as the date of the subject's last clinic visit in the study.

• If only the year is known, the stop date will be imputed as "31-Dec" of that year or as the date of the subject's last clinic visit in the study if in the same year.

QMD Ref: Worldwide-TMP-ST-005-7.0 Effective: 12Aug2019 Governing QMD: Worldwide-SOP-ST-0		
Confidentiality Statement		
This document is the property of Worldwide Clinical Trials Inc. and may not be duplicated, copied, altered or removed from company without prior approval from Worldwide Quality Assurance or in compliance with Worldwide Standard Operating Procedures.		

Worldwide Clinical Trials Controlled Quality Management Document		
WORLDWIDE	Sponsor:	Veru Inc.
CLINICAL TRIALS	Protocol Number:	V0211901
STATISTICAL ANALYSIS PLAN. PHASE 2-3-4		

• If the month and year are known, the stop date will be imputed as the last day of that month unless the stop date corresponds to the same month as the subject's last clinic visit in which case the date of subject's last clinic visit in the study will be used instead.

#### Missing start date will be imputed as follows:

- If the stop date occurs on or after the start of study drug or the event / concomitant medication is ongoing, the start date will be imputed as the date of the first dose of study drug.
- If the stop date occurs before the start of study drug, the start date of the event / concomitant medication will be imputed as the subject's screening date or the stop date of the event / concomitant medication whichever the earlier.

# Partial start date (year present, but month and day missing)

- If the stop date occurs on or after the start of study drug or the event / concomitant medication is ongoing, and the year is the same as the year of first dosing the start date will be imputed as "01-Jan" of the same year or the date of the first dose of study drug whichever is latest. If the year is different from the year of first dosing "01-Jan" will be used.
- If the stop date occurs before the start of study drug, the start date of the event / concomitant medication will be imputed as the "01-Jan" of the same year.

#### Partial start date (month and year present, but day missing)

- If the stop date occurs on or after the start of study drug or the event / concomitant medication is ongoing, the start date will be imputed as the first day of the same month and year unless this partial start date is in same month as the first dose of study drug in which case the date of first dose of study drug will be used.
- If the stop date occurs before the start of study drug, the start date will be imputed as the first day of the month and year of the partial stop date.

If the start time is missing it will be imputed only in the case where the start date of the concomitant medication / event corresponds to the date of the first dose of study drug. The time will be imputed as the same time as the first dose of study drug. In all other cases the time will not be imputed.

# 6.2.5 Missing Last Dates of Study Drug Dosing

Missing dates for study drug dosing will not be imputed.

# **6.2.6** Missing Diagnosis Dates

QMD Ref: Worldwide-TMP-ST-005-7.0 Effective: 12Aug2019	Governing QMD: Worldwide-SOP-ST-001	
Confidentiality Statement		
This document is the property of Worldwide Clinical Trials Inc. and may not be duplicated, copied, altered or removed from company without		
prior approval from Worldwide Quality Assurance or in compliance with Worldwide Standard Operating Procedures.		

Worldwide Clinical Trials Controlled Quality Management Document		
WORLDWIDE CLINICAL TRIALS	Sponsor:	Veru Inc.
WORLDWIDE CLINICAL TRIALS	Protocol Number:	V0211901
STATISTICAL ANALYSIS PLAN. PHASE 2-3-4		

If the month and year are present but the day is missing, the diagnosis date will be set to first day of the relevant month. If only the year is recorded the diagnosis date will be set as "01-Jan" for that year.

# **6.2.7** Exposure to Study Drug

Exposure to study drug will be calculated as the date of last dosing minus the first day of dosing + 1. The exposure calculation will not take into account breaks in therapy.

#### **6.2.8** Inexact Values

In the case where a variable is recorded as "> x", " $\geq$  x", " $\leq$  x", or " $\leq$  x", a value of x will be taken for analysis purposes.

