7.2.2 Placebo Control

Placebo capsules contain zero (0) mg VERU-111 drug substance will be supplied in bottles containing 21 capsules each. The placebo capsules will contain only anhydrous lactose, USP. These capsules are identically appearing to the VERU-111 capsules. Patients will take one Placebo capsule per day.

The Placebo capsules should be stored at controlled room temperature, 20°C to 25°C (68°F to 77°F) with excursions permitted between 15°C to 30°C (59°F to 86°F).

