# **6.13 Pharmacokinetic Analyses**

The pharmacokinetics of VERU-111 will be assessed on Day 15. Plasma samples for pharmacokinetic assessment will be taken at baseline (prior to dosing on Day 15) and at 4 hours (±2 hours), 12 hours (±2 hours) after dosing on Day 15, and at 24 hours (±2 hours) after dosing on Day 15 (prior to dosing on Day 16).

The following parameters will be estimated through standard methodology with this limited sampling schedule:

• AUC0-t Area Under Concentration Curve from time 0 to time t.

• Cmax Maximum Concentration

•  $T_{max}$  Time to  $C_{max}$ 

• kel Elimination Rate Constant

QMD Ref: Worldwide-TMP-ST-005-7.0 Effective: 12Aug2019	Governing QMD: Worldwide-SOP-ST-001	
Confidentiality Statement		
This document is the property of Worldwide Clinical Trials Inc. and may not be duplicated, copied, altered or removed from company without		
prior approval from Worldwide Quality Assurance or in compliance with Worldwide Standard Operating Procedures.		

Worldwide Clinical Trials Controlled Quality Management Document		
WORLDWIDE CLINICAL TRIALS	Sponsor:	Veru Inc.
	Protocol Number:	V0211901
STATISTICAL ANALYSIS PLAN. PHASE 2-3-4		

Cl/F Clearance
T1/2 Half-Life

• Vd/F Volume of Distribution

The limited sampling schedule is used due to limitations on study personnel entering the subject's room during the day. If the sample is missed due to restrictions in entering the room, then this sample will be listed as missing.

PK concentrations will be summarized using descriptive statistics (n, mean, standard deviation, CV(%), geometric mean, median, minimum and maximum) for absolute values by treatment group and visit. Mean plots by treatment and individual subject curves will be displayed on linear and semi-logarithmic scale (time on linear scale, concentration on logarithmic scale) for concentration data.

PK parameters will be summarized using descriptive statistics (n, mean, standard deviation, median, minimum and maximum) for absolute values by treatment group.

All PK concentration and PK parameter data will be listed.

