**Confidentiality Statement** 

#### 

Table Number	Table Title	Included in Preliminary Analysis	Included in DSMB (Table No.)	Validation Method	Shell Number (if repeat)
14.4.1.1	Pharmacokinetic Concentrations Descriptive Statistics (ITT Population)			IP	
14.4.2.1	Pharmacokinetic Parameters Descriptive Statistics (ITT Population)			IP	

QMD Ref: Worldwide-TMP-ST-005-7.0 Effective: 12Aug2019

Governing QMD: Worldwide-SOP-ST-001

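### SAP 6.2.8 sets censored results to their limit without exempting plasma VERU-111 levels, and 6.13 has no below-limit rule, so below-limit samples, if recorded as '<x', would distort the PK summaries

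*SAP*

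**What the plan says.** SAP 6.2 introduces its rules with "This section describes the derivations required for statistical analysis". Within it, 6.2.8 handles results reported only as above or below some x: "a value of x will be taken for analysis purposes". No variable is exempted. The opening of 6.2 has one limiting clause, that unless otherwise stated "variables derived in the source data will not be re-calculated".

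SAP 6.13 takes Day 15 samples before dosing and then "at 4 hours (±2 hours), 12 hours (±2 hours) after dosing on Day 15, and at 24 hours (±2 hours". On method it says only "The following parameters will be estimated through standard methodology with this limited sampling schedule"; the list is AUC0-t, Cmax, Tmax, kel, Cl/F, T1/2 and Vd/F. It deals with a missed sample, which is listed as missing, but not with a sample that was assayed and fell below the limit.

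On presentation, 6.13 says "PK parameters will be summarized using descriptive statistics (n, mean, standard deviation, median, minimum and maximum) for absolute values by treatment group", and it asks for concentration summaries by treatment group and mean plots by treatment. SAP 6.3 names two groups, VERU-111 18 mg and Placebo. The list of tables in SAP section 11 carries "Pharmacokinetic Parameters Descriptive Statistics (ITT Population" as table 14.4.2.1, with a matching concentration table 14.4.1.1. SAP 6.1.3 defines ITT as all randomized subjects, and no PK population is defined. Protocol 8.5 and 9.6 schedule PK sampling without distinguishing the arms, while Protocol 7.2.2 states "Placebo capsules contain zero (0) mg VERU-111 drug substance".

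**The concern.** Setting a value to its limit may do little harm for a safety laboratory result. It is a poor rule for drug concentrations. A below-limit result in a subject given no drug means no detectable drug, and the rule turns it into a measured level. In a treated subject, kel, T1/2 and Vd/F depend on the slope of log concentration over at most three post-dose samples. Raising the last of them to the limit bends that slope towards zero.

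Day 15 pharmacokinetics is a listed secondary endpoint. If the rule operates, the Placebo column of the PK tables would show exposure to a drug those subjects never received. In the VERU-111 arm, half-life and trough would be shifted up and kel down, by an amount set by the assay rather than by the drug.

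**Working it through.** The plan states no LLOQ, half-life or expected concentration, so there is no figure of its own to reproduce.

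**Inputs from the documents.** Sampling pre-dose and at 4, 12 and 24 h (SAP 6.13); 18 mg once daily (SAP 1); a censored value is set to x (SAP 6.2.8).

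**Assumptions.** Below-limit results arrive as '<LLOQ'; mono-exponential decline from 4 h; pre-dose level equal to the 24 h level; t = 24 h in AUC0-t, because the SAP leaves t open. Concentrations are in units of LLOQ, and R = C(4h)/LLOQ.

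**Placebo, all four samples below the limit.** Every concentration becomes x, so Cmax = x and kel = 0, and T1/2 is undefined. AUC0-24 = x(4 + 8 + 12) = 24x. If x were 1 ng/mL (an assumption) and the nominal dose were used, Cl/F = 18,000,000 ng / 24 ng·h/mL = 750 L/h, in a subject who received no drug.

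**VERU-111 arm, when it matters.** The 24 h level is R·2^(-20/T), where T is the true half-life. It is below LLOQ only if T < 20/log2(R):

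| R | 24 h sample below limit if T is under |
|---|---|
| 5 | 8.6 h |
| 10 | 6.0 h |
| 20 | 4.6 h |
| 50 | 3.5 h |
| 100 | 3.0 h |

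Above these values no post-dose sample is altered and the bias is zero (for example T = 12 h at every R in the table).

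**VERU-111 arm, how much.** kel comes from least squares of ln C on time. The mean time is 40/3 = 13.33 h, the deviations are -9.33, -1.33 and 10.67, and their sum of squares is 202.67.

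- T = 4 h, R = 10: true levels are 10, 2.5 and 0.3125, and the last is set to 1. Logs are 2.303, 0.916 and 0. Slope = (-9.33 x 2.303 - 1.33 x 0.916)/202.67 = -0.1121. Estimated half-life = 0.693/0.1121 = 6.2 h, or 1.55 times the truth.
- T = 5.05 h, R = 3: levels are 3, 1.0006 and 0.193, and the last is set to 1. Slope = -9.33 x 1.0986/202.67 = -0.0506. Estimated half-life = 13.7 h, or 2.7 times the truth.

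Other cases by the same formula:

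| R | True T | Estimated | Ratio |
|---|---|---|---|
| 5 | 4 h | 9.2 h | 2.29 |
| 5 | 6 h | 8.8 h | 1.47 |
| 10 | 3 h | 6.4 h | 2.12 |
| 20 | 4 h | 4.7 h | 1.17 |

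On a fine grid over T = 3-6 h and R = 3-50, with the 12 h sample quantifiable and the 24 h sample below the limit, the ratio runs from 1.0 to about 2.7. It can be larger if the 12 h sample is below the limit too (R = 5, T = 3 h: 9.35 h, ratio 3.1). In 58,883 random scenarios with at least one below-limit sample the ratio was never below 1, so the direction is firm.

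**Effect of excluding the below-limit 24 h sample.** For T = 4 h, R = 10, kel = ln(10/2.5)/8 = 0.1733 and T1/2 = 4.0 h, the true value. If the 12 h sample is below the limit as well, only one point remains and half-life cannot be estimated.

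**Would zero be better than x for AUC?** By linear trapezoid for T = 6 h, R = 10 (levels 0.992 pre-dose, 10, 3.969, 0.992), the true-concentration AUC0-24 is 21.98 + 55.87 + 29.76 = 107.62. Setting the below-limit values to x gives 107.69 (+0.1%); setting them to 0 gives 99.69 (-7.4%). For T = 4 h, R = 10, the true value is 87.5, x gives 93.0 (+6.3%) and 0 gives 85.0 (-2.9%). Neither substitution is uniformly better.

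**The case against.** The strongest reply is that nothing shows the harm will occur. Sampling is scheduled in both arms, but the documents never say that placebo plasma is assayed. Below-limit results may arrive as a text code, which 6.2.8 would not touch. Protocol 9.6.1 defers method validation and sample analysis to the final report. The parameters are to be estimated by standard methodology, and variables derived in the source data are not re-calculated. If kel and half-life are delivered ready-made, 6.2.8 never enters the fit.

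Much of this stands. A reader might infer that placebo subjects will be reported with VERU-111 exposure and that active-arm half-lives will come out too long. The documents support neither as a certainty; both depend on conditions they leave open.

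The reply does not remove the point. 'Standard methodology' is undefined and is not said to override 6.2.8, which is the only written rule for censored results. The clause on source-derived variables could protect delivered parameters, but not the concentration tables and mean plots, where '<x' is raw data.

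It is also fair that little rests on this. PK is descriptive with no test attached. Because dosing stops at discharge, Day 15 PK comes from a subset of about 20 active subjects. A placebo profile flat at the limit would be recognisable in the planned individual curves and listings. That limits the importance of the point; it is not a reason to leave the rule as written.

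**Conclusion.** The point holds in conditional form. Applied literally to a plasma result recorded as '<x', the SAP's rule gives a wrong value, and nothing in 6.13 prevents it.

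- **Placebo:** if samples are assayed and reported as '<x', each is tabulated at x, and a subject with four such samples gets AUC0-24 = 24x. No half-life assumption is needed.
- **VERU-111 arm:** if a 12 h or 24 h sample is below the limit and 6.2.8 is applied before kel is fitted, the estimated half-life is too long. The illustration is 6.2 h for a true 4 h at R = 10, and up to about 2.7-fold over half-lives of 3-6 h and R of 3-50 with the 12 h sample quantifiable. If no active sample is below the limit, the bias is zero.

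Without an LLOQ or half-life in the documents, neither the occurrence nor the size of the active-arm bias can be established. The text of 6.2.8 as read here shows the 'less than or equal' sign twice and no plain 'less than'; this is taken to be a reading fault, with '<x' covered. Only a descriptive secondary endpoint is affected, and efficacy conclusions do not change.

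**What to change.** - In 6.2.8, add that the rule does not apply to plasma VERU-111 concentrations.
- In 6.13, state that AUC0-t runs to the last quantifiable sample, and that below-limit samples after it are excluded from kel, T1/2 and Vd/F. Report half-life as not estimable when too few points remain.
- In 6.13, prespecify one below-limit convention for the concentration summaries, and say how a below-limit pre-dose value enters AUC. Substituting zero is not urged here, since it can do worse than x on AUC.
- Restrict PK tables 14.4.1.1 and 14.4.2.1 and PK figures 14.4.1.1 and 14.4.1.2 to subjects who received VERU-111, and list any placebo results separately.

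The cost is a few sentences and four output titles; no new data are needed. The one real downside is that half-life will not be estimable for some subjects. Where only the 4 h and 12 h samples remain, it rests on two points with no residual check of fit.
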